11.4.2.6. Study Drug Compliance

As the study drug will be administered under direct supervision at the study site, no analysis of compliance will be performed.

11.4.3. Efficacy Analysis

As efficacy is not being measured in this study, no efficacy analysis will be performed.

11.4.4. Safety Analysis

The overall safety profile of SKL24741, relative to placebo, will be assessed in terms of the following safety endpoints:

- Incidence of treatment-emergent adverse events
- Clinical laboratory values (hematology, coagulation, clinical chemistry, urinalysis and cholesterol)
- ECG outcomes
- Vital signs
- Peak expiratory flow rate (PEFR)
- Columbia-Suicide Severity Rating Scale (C-SSRS) (Part B only)

Statistical analysis details will be provided in the SAP. Safety analyses will be based on the Safety analysis set.

All safety data will also be presented in individual subject data listings.

11.4.4.1. Adverse Events

Adverse events will be coded according to Medical Dictionary for Regulatory Activities (MedDRA). The number and percentage of subjects experiencing an adverse event will be summarized by the MedDRA system organ class and preferred term, as well as by dose received. Adverse events will be classified as pre-treatment or treatment-emergent.

Pre-treatment adverse events are defined as adverse events that were reported or worsened after signing the ICF up to start of study medication.

Treatment-emergent adverse events are defined as adverse events that were reported or worsened on or after start of study medication through the Follow-up visit.

Only treatment-emergent adverse events will be summarized in tables. Treatment-emergent adverse events will hereafter be referred to as “adverse events.”

The incidence of adverse events will be summarized. Adverse event summaries will include the following:

- All adverse events (regardless of severity or relationship to study drug)
- SAEs
- Adverse events by severity
- Adverse events by relationship to study drug
- Adverse events leading to discontinuations
- Adverse events leading to deaths

Adverse event summaries will be presented by MedDRA System Organ Class and Preferred Term. A subject with multiple occurrences of the same adverse event or a continuing adverse event will be counted once, and only the maximum severity level will be presented in the severity summaries, and the worst relationship level in the relationship summaries.

Adverse events will be listed separately for those leading to death, SAEs, dose interruption, and permanent discontinuation.

All adverse events through the Follow-up visit will be listed in an individual subject data listing, including pre-treatment adverse events.

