6. STUDY ENDPOINTS

6.1. Primary Endpoint

Safety and tolerability will be based on assessment of adverse events, clinically significant laboratory assessments, electrocardiograms (ECGs), vital signs (blood pressure, heart rate, body temperature, respiratory rate, arterial oxygen saturation (SaO₂) (using pulse oximetry)), physical examinations, peak expiratory flow rate (PEFR), and Columbia-Suicide Severity Rating Scale (C-SSRS) (Part B only).

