12.1.1.2. Causality Assessment

An assessment should be made of the causal relationship of the adverse event to the study treatment, i.e., according to the following definitions in [Table 12](#).

Table 12: Definitions of Causality Assessment

Causality Assessment	Definitions
Unrelated	The event is occurring before dosing The event is definitely produced by the subject's clinical state or by other modes of therapy administered to subject
Remote	The event does not follow a reasonable (poor) temporal relationship with drug treatment And/or the event is readily explained by the subject's clinical state or by other modes of therapy administered to subject
Possible	Reasonable temporal relationship with drug treatment But the event could have been produced by the subject's clinical state or by other modes of therapy administered to subject
Probable	Reasonable temporal relationship with drug treatment, abates upon discontinuation of drug And/or event cannot be reasonably explained by the known characteristics of the subject's clinical state.
Definite	Distinct temporal relationship with drug treatment, abates upon discontinuation of drug (de-challenge) and is confirmed by reappearance of the reaction on repeat exposure (re-challenge)

Adverse events must be followed until resolution by the Principal Investigator. Resolution is defined as the return to baseline status or stabilization of the condition with the expectation that it will remain chronic. Adverse events that are not serious and are ongoing at the subject's last visit will be followed for a maximum of 30 days. Serious adverse events that are not resolved or stabilized during this time period will be followed until resolution or stabilization.

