12.1.2. Routine Reporting

For the purposes of this study, the period of observation of adverse events for each subject extends from the signing of the informed consent form until their last visit including the follow-up visit or early termination, whichever is longer.

All events reported by the subject, observed by the clinical staff (events, such as abnormal, clinically significant findings from physical examinations, ECG tracings, laboratory assessments, and vital sign measurements), or elicited by general questioning will be recorded in the Institution's source document and reported as an adverse event and captured in the adverse events CRF. If necessary, every effort will be made to obtain an adequate

follow-up of the subjects. Should any subject choose to withdraw early from the study, they will be advised of the safety precautions to be taken.

Early Termination and End of Study (EOS) visit assessments should be performed, including the following: medical history, vital signs, physical exam, safety and clinical laboratory tests, ECG, peak expiratory flow rate (PEFR), Columbia-Suicide Severity Rating Scale (C-SSRS), and adverse event/concomitant monitoring.

Subjects will be questioned on their health status at the beginning of each visit and before their departure from the clinical site. Open-ended questions will be asked.

Classification will be performed by System Organ Class (SOC) and Preferred Term (PT) using the latest version of Medical Dictionary for Regulatory Activities (MedDRA) at the start of the study.

In general, AEs occurring secondary to other events (e.g., clinical sequelae or a cascade of events) should be identified by their primary cause. For example, if severe vomiting is known to result in dehydration, it is sufficient to record only vomiting as SAE or AE in the CRF. However, medically significant AEs occurring secondary to an initiating event that are separated in time should be recorded as independent events on the CRF.

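### Pre-treatment and treatment-emergent adverse events are separated by when they were reported or worsened, not by onset, so a pre-dose event first reported after dosing is tabulated as treatment-emergent

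*Protocol*

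**What the plan says.** Section 11.4.4.1 of the protocol sorts every adverse event into one of two classes. For the first: "Pre-treatment adverse events are defined as adverse events that were reported or worsened after signing the ICF up to start of study medication". For the second: "Treatment-emergent adverse events are defined as adverse events that were reported or worsened on or after start of study medication through the Follow-up visit". It then limits the tables to the second class: "Only treatment-emergent adverse events will be summarized in tables". All adverse events, including pre-treatment ones, still appear in an individual subject listing.

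The classification feeds the main safety results. Section 11.4.4 lists "Incidence of treatment-emergent adverse events" first among the safety endpoints, and Section 6.1 opens the primary endpoint with adverse events: "Safety and tolerability will be based on assessment of adverse events, clinically significant laboratory assessments".

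Collection starts well before dosing. Under Section 12.1.2, "the period of observation of adverse events for each subject extends from the signing of the informed consent form", and screening may begin on Day -28.

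**The concern.** The date of a report is a property of data collection. The date of onset is what separates an event that could be due to the drug from one that could not. By keying both classes to reporting, the protocol lets a late report move a pre-dose event into the treatment-emergent tables.

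The protocol's own schedule offers a route for this. Laboratory samples are taken on Day -1, and triplicate ECGs are recorded at 0.75, 0.5 and 0.25 hours before the Day 1 dose and analysed by a central ECG laboratory (Tables 1 and 2, Section 10.6.4). Clinically significant abnormal findings become adverse events (Sections 11.4.4.2 and 11.4.4.3). A pre-dose abnormality that is read and reported only after dosing would then be treatment-emergent by the printed rule.

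What is at stake is the adverse event incidence at each dose level, in cohorts small enough for a single subject to be visible.

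**Working it through.** The protocol states no figure that depends on this definition, so there is nothing to reproduce. The check is a reading of the rules, followed by simple arithmetic for scale.

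**Step 1: apply the two definitions to two cases.**

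| Case | Pre-treatment rule | Treatment-emergent rule | Result |
|---|---|---|---|
| Onset after consent and before dose; first reported after dose; never worsens | Not met: neither reported nor worsened before dose | Met: reported after dose | Tabulated as treatment-emergent |
| Reported before dose; worsens after dose | Met: reported before dose | Met: worsened after dose | In both classes, though the section treats them as alternatives |

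**Step 2: compare with the protocol's other timing rules.** Table 12 in Section 12.1.1.2 gives as one ground for a rating of unrelated: "The event is occurring before dosing". That is a test of occurrence, not of reporting. Section 11.4.2.4 separates prior from concomitant medication by start and end dates. So the first case above could be tabulated as treatment-emergent and also be unrelated because it preceded dosing.

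**Step 3: check for an override.** No other section supplies an onset rule. The protocol leaves the definition of baseline to the SAP (Sections 11.4.4.2 to 11.4.4.4, 11.4.4.6 and 11.4.4.7), but it writes the treatment-emergent definition itself. A SAP that used onset would depart from the protocol.

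**Step 4: effect of one misclassified subject.** Group sizes are from Section 7.1 and Table 4. The shift is 100/n percentage points, in any table row where that subject would not otherwise be counted.

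| Group | n | Shift |
|---|---|---|
| Part A active, one dose | 4 | 100/4 = 25.0 |
| Part B active, one dose | 6 | 100/6 = 16.7 |
| Placebo, one cohort (either part) | 2 | 100/2 = 50.0 |
| Placebo pooled, Part A | 10 × 2 = 20 | 100/20 = 5.0 |
| Placebo pooled, Part B | 4 × 2 = 8 | 100/8 = 12.5 |

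**Step 5: how often.** The documents give no rate of late-reported pre-dose events, so no expected count can be derived from them. Purely for scale, let p be the chance that a subject has such an event. The chance of at least one in a group of n is 1 − (1 − p)^n. For n = 4 this is 3.9%, 18.5% or 34.4% at p = 1%, 5% or 10%. For n = 6 it is 5.9%, 26.5% or 46.9%. These values of p are assumptions, and nothing in the protocol supports one over another.

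**The case against.** **Frequency.** Section 12.1.2 says: "Subjects will be questioned on their health status at the beginning of each visit and before their departure from the clinical site". A reader might infer that a subject questioned on admission at Day -1 is not asked again until discharge on Day 4 or Day 17, so that pre-dose complaints would often surface only after dosing. The protocol does not support that. Tables 1 and 2 make adverse event assessment ongoing from consent. Section 12.1.2 also records events that subjects volunteer or staff observe, and Section 9.3 requires pre-dose vital signs, PEFR and ECG before the drug is given. Section 12.1.1 further narrows the exposure: a condition present at study start is an adverse event only if it worsens. Affected events should therefore be uncommon, and that part of the objection stands.

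**Direction.** A reader might also infer a bias against the drug. In the randomised, blinded cohorts a pre-dose event cannot depend on the arm, so in expectation the error favours neither. The analysis is descriptive, and adverse events are one of several components of the primary endpoint. The numerical rule in Section 7.3 for discontinuing dosing counts only related or possibly related events, so an event rated unrelated because it preceded dosing does not enter it. The tables by relationship and the listings would also show that rating. All of this limits the harm.

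**Wording.** *Reported* may be loose drafting for *occurred*. Section 11.4.2.3 uses the word of medical history in a way that must mean occurrence. The reading is plausible, but it does not remove the problem: the printed rule governs every adverse event table, a programmer may apply it as written, and the overlap between the classes remains for an event that begins before dosing and worsens afterwards.

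**Conclusion.** The point holds as a defect in a definition that the protocol fixes itself. Both classes omit onset, a pre-dose event reported late is literally treatment-emergent, and an event that worsens after dosing can fall in both classes. The consequence is occasional over-counting that is non-differential between randomised arms.

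The size is set by the cohorts: 25.0 points per misclassified subject in a Part A active dose group and 16.7 points in a Part B one. These figures describe what one such event does, not how many there will be. The conclusion rests on the literal wording and on the absence of an onset rule elsewhere in the protocol. It does not rest on any assumed frequency. The correction is worth making because it is cheap and every adverse event table depends on it.

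**What to change.** In Section 11.4.4.1, replace the two definitions:

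- **Treatment-emergent:** an adverse event with onset at or after the first dose, or a pre-dose event that worsens in severity at or after the first dose, through the Follow-up visit.
- **Pre-treatment:** an adverse event with onset after consent and before the first dose, without later worsening.

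This makes the classes mutually exclusive and brings them into line with the timing test in Table 12. The handling of an unknown onset time on Day 1 can be left to the SAP; counting such events as treatment-emergent would be a cautious choice.

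The cost is two sentences in the protocol, plus onset clock time for events that start on Day 1. The eCRF completion guidelines are a separate document, so whether that time is already collected cannot be checked here.

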11.4.4.2. Clinical Laboratory Assessments

All statistical analyses of laboratory values will be performed using International System of Units (SI). Hematology, coagulation, clinical chemistry, urinalysis, and cholesterol panel results will be summarized by dose received and by part of the study at each scheduled time point.

The raw values, changes from baseline, percentage change from baseline (for selected laboratory parameters), shifts from baseline (categorical change from baseline), and clinical abnormalities will be summarized as appropriate. Baseline will be defined in the study SAP. Clinically significant abnormal findings will be reported as adverse events.

11.4.4.3. Electrocardiogram

A summary of raw values and change from baseline values (as specified in the study SAP) will be provided by treatment group, dose received, and by part of the study at each scheduled visit for the following ECG measurements: heart rate (HR), RR, PR, QT, QTc intervals, and QRS duration. In addition, the number and percentage of subjects by maximum on-treatment value of QT/QTc intervals, categorized as ≤ 450 msec, >450 msec and ≤ 480 msec, >480 msec and ≤ 500 msec, and >500 msec, as well as maximum on-treatment change from baseline value of QT/QTc intervals, categorized as ≤ 30 msec, >30 msec and ≤ 60 msec, and >60 msec, will be provided. Baseline will be defined in the study SAP. Correction of the QT values will be done using Fridericia formula. Clinically significant abnormal findings will be reported as adverse events.

11.4.4.4. Vital Signs

The following vital signs will be summarized by treatment group at each scheduled time point: systolic and diastolic blood pressure (mmHg) measurements (in supine and standing in the same sequence in each subject, in order to allow orthostatic measurements), body temperature ($^{\circ}\text{C}$), heart rate (beats per minute [bpm]), respiratory rate (breaths per minute), and arterial oxygen saturation (SaO_2) (using pulse oximetry). The raw values, changes from baseline, percentage change from baseline (for selected parameters), shifts from baseline (categorical change from baseline), and clinical abnormalities will be summarized as appropriate. Baseline will be defined in the study SAP. Clinically significant abnormal findings in vital signs will be reported as adverse events.

11.4.4.5. Physical Examination

Physical examination findings at screening will be presented as a listing only. At post-screening assessments, any untoward findings identified during physical examinations will be captured as adverse events, if those findings meet the definition of an adverse event.

11.4.4.6. Peak Expiratory Flow Rate

Peak expiratory flow rate (PEFR) results will be summarized by treatment group and by part of the study at each scheduled time point. The raw values, changes from baseline, percentage change from baseline, shifts from baseline (categorical change from baseline), and clinical abnormalities will be summarized as appropriate. Baseline and unit (e.g., L/min) will be defined in the study SAP. Clinically significant abnormal findings will be reported as adverse events.

11.4.4.7. Columbia-Suicide Severity Rating Scale (Part B only)

Columbia-Suicide Severity Rating Scale (C-SSRS) results will be summarized by treatment group and by part of the study at each study day of assessment. The raw values, changes from baseline, and clinical abnormalities will be summarized as appropriate. Baseline will be defined in the study SAP. Clinically significant abnormal findings will be reported as adverse events.

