10.6.5. Columbia-Suicide Severity Rating Scale

The Columbia-Suicide Severity Rating Scale (C-SSRS) is a brief questionnaire that provides for the identification, quantification, and standardized assessment of the occurrences and severity of suicidal ideation and behavior. The C-SSRS will be assessed only after multiple dose administration (Part B). The “Baseline (Lifetime/Recent)” version of the C-SSRS will be assessed at screening ([Appendix C](#)). The C-SSRS “Since Last Visit” version will be assessed on other study days ([Appendix D](#)).

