
Ask questions 1 and 2. If both are negative, proceed to "Suicidal Behavior" section. If the answer to question 2 is "yes", ask questions 3, 4 and 5. If the answer to question 1 and/or 2 is "yes", complete "Intensity of Ideation" section below.
 
1. Wish to be Dead Subject endorses thoughts about a wish to be dead or not alive anymore, or wish to fall asleep and not wake up. Have you wished you were dead or wished you could go to sleep and not wake up?
 
If yes, describe:
		
Lifetime: Time He/She Felt Most Suicidal
 
 
 Yes	No	Yes	No	
 
 				
 
 
2. Non-Specific Active Suicidal Thoughts General non-specific thoughts of wanting to end one's life/commit suicide (e.g., "I've thought about killing myself") without thoughts of ways to kill oneself/associated methods, intent, or plan during the assessment period. Have you actually had any thoughts of killing yourself?
 
If yes, describe:
		Yes	No	Yes	No				
Yes	No	Yes	No								
											

3. Active Suicidal Ideation with Any Methods (Not Plan) without Intent to Act Subject endorses thoughts of suicide and has thought of at least one method during the assessment period. This is different than a specific plan with time, place or method details worked out (e.g., thought of method to kill self but not a specific plan). Includes person who would say, "I thought about taking an overdose but I never made a specific plan as to when, where or how I would actually do it...and I would never go through with it." Have you been thinking about how you might do this?
 
If yes, describe:
		
 
 Yes	No	Yes	No	
 
 				
 
		Yes	No	Yes	No				
Yes	No	Yes	No								
											

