
4. Active Suicidal Ideation with Some Intent to Act, without Specific Plan Active suicidal thoughts of killing oneself and subject reports having some intent to act on such thoughts, as opposed to "I have the thoughts but I definitely will not do anything about them." Have you had these thoughts and had some intention of acting on them?
 
If yes, describe:
		
 
 Yes	No	Yes	No	
 
 				
 
		Yes	No	Yes	No				
Yes	No	Yes	No								
											

5. Active Suicidal Ideation with Specific Plan and Intent Thoughts of killing oneself with details of plan fully or partially worked out and subject has some intent to carry it out. Have you started to work out or worked out the details of how to kill yourself? Do you intend to carry out this plan?
 
If yes, describe:
		
 
 Yes	No	Yes	No	
 
 				
 
		Yes	No	Yes	No				
Yes	No	Yes	No								
											
INTENSITY OF IDEATION											

The following features should be rated with respect to the most severe type of ideation (i.e., 1-5 from above, with 1 being the least severe and 5 being the most severe). Ask about time he/she was feeling the most suicidal.
 
Lifetime - Most Severe Ideation: _____
 
Past X Months - Most Severe Ideation: _____
		
Most Severe
	
Most Severe
								

Frequency How many times have you had these thoughts?
 
(1) Less than once a week (2) Once a week (3) 2-5 times in week (4) Daily or almost daily (5) Many times each day
											

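### The planned C-SSRS change from baseline compares two forms with different recall windows, so it mixes window length with change over time

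*Protocol*

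**What the plan says.** Section 10.6.5 of the protocol ties the form to the visit. The Lifetime/Recent "version of the C-SSRS will be assessed at screening", and the Since Last Visit "version will be assessed on other study days". Table 2 marks C-SSRS at screening, on one day around the end of dosing (Day 15 as I read the table, though the column alignment is uncertain) and at Follow-up. Neither Day -1 nor Day 1 is marked.

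Section 11.4.4.7 then plans the summary by treatment group and assessment day: "The raw values, changes from baseline, and clinical abnormalities will be summarized as appropriate". It adds: "Baseline will be defined in the study SAP". Clinically significant findings are also to be reported as adverse events.

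The forms are reproduced in Appendices D and E (Section 10.6.5 cites them as C and D). The screening form has a lifetime column, "Lifetime: Time He/She Felt Most Suicidal", and a recent column, "Past X Months - Most Severe Ideation", in which X is not filled in. The number of years in its recent column for suicidal behavior is blank too. On scoring, the form says: "The following features should be rated with respect to the most severe type of ideation".

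**The concern.** A change from baseline means something when the same quantity is measured the same way at two times. Here the baseline value is the worst ideation over a lifetime or over an unstated number of months, and the later value is the worst over a few weeks. With no change in the subject, the longer window gives an equal or higher expected score. A negative difference can therefore reflect the form and not the drug.

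C-SSRS is one component of the Part B primary safety endpoint (Section 6.1) for a CNS-active compound. Part B has 4 x 6 = 24 active and 4 x 2 = 8 placebo subjects. Positive scores should be rare, so one or two subjects with a past history could dominate a cohort's mean change. Sections 8.1 and 8.2 contain no explicit exclusion for past ideation or a positive screening C-SSRS, so non-zero baselines are possible.

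**Working it through.** The protocol gives no figure for this scale, so there is nothing to reproduce. The check has four steps.

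**1. What the SAP can choose from.** Screening is the only pre-dose assessment (Table 2), and it uses the Lifetime/Recent form (Section 10.6.5). Any baseline must come from that form's lifetime or recent column. No pre-dose Since Last Visit record exists.

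**2. Window of the first post-dose form.** Take last visit to mean the last C-SSRS, the post-dose day to be Day 15, and no Day 0.
- Screened on Day -28: 28 + 15 - 1 = 42 days, of which 28 are before dosing (28/42 = 67%).
- Screened on Day -2: 2 + 15 - 1 = 16 days, of which 2 are before dosing (2/16 = 12.5%).

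The form can therefore include a good deal of pre-dose time.

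**3. Effect on individual scores.** Of the 5 x 5 = 25 combinations of baseline 1-5 and on-treatment 1-5, 15 give a difference of zero or less and 10 a positive one. A subject with baseline 0 and any on-treatment ideation always shows a positive difference. As an illustration, take six active subjects with baselines 3, 4, 0, 0, 0, 0 and on-treatment scores 0, 2, 1, 0, 0, 0. The differences are -3, -2, +1, 0, 0, 0, with mean -4/6 = -0.67, although two of the six have on-treatment ideation.

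**4. Expected size with no drug effect.** These assumptions are mine, not the protocol's:
- ideation episodes are Poisson at 0.02 or 0.05 per person-year;
- severities 1 to 5 have probabilities 0.50, 0.25, 0.12, 0.08 and 0.05;
- lifetime recall covers 20 years.

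With rate r, window T years, and c_j the probability that one episode has severity at most j (c_0 to c_4 = 0, 0.50, 0.75, 0.87, 0.95), the expected worst score is

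E = sum over j = 0 to 4 of [1 - exp(-rT(1 - c_j))].

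For the lifetime column at r = 0.02, rT = 0.4 and E = 0.330 + 0.181 + 0.095 + 0.051 + 0.020 = 0.677. For a 42-day post-baseline window E = 0.004, so the expected change is -0.67. At r = 0.05, rT = 1 and E = 0.632 + 0.393 + 0.221 + 0.122 + 0.049 = 1.417, giving -1.41. A simulation under the same assumptions agrees.

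| Baseline window | Expected change, no drug effect (16 to 42 days; both rates) | Subjects with a negative difference |
|---|---|---|
| Lifetime (20 years) | -0.67 to -1.41 | 33% to 63% |
| 12 months | -0.03 to -0.09 | 2% to 5% |
| 6 months | -0.01 to -0.04 | 1% to 2.5% |
| 1 month | within 0.004 of zero | under 0.5% |

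With a lifetime baseline, about 23% (lower rate) to 45% (higher rate) of subjects who do have post-baseline ideation would show a difference of zero or less. With 12 months this falls to about 1% to 3%.

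**The case against.** A reader might infer that the protocol subtracts a lifetime score from a since-last-visit score and so hides ideation on drug. The text does not support that.

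- **No column is named.** Section 11.4.4.7 leaves the baseline definition to the SAP, and its qualifier lets the SAP omit the change score. The large figures above apply only if the lifetime column is chosen.
- **Ideation stays visible.** The same sentence plans raw values and clinical abnormalities. Section 11.4.4 puts all safety data in subject listings, and clinically significant findings become adverse events. A post-dose level 2 would be seen whatever its difference from screening.
- **No improved category is planned.** Sections 11.4.4.2, 11.4.4.4 and 11.4.4.6 list shifts from baseline for other measures; Section 11.4.4.7 does not.
- **Placebo subjects complete the same forms.** The artefact is expected equally in both groups, and Section 11.4.4 assesses safety relative to placebo.
- **Adverse events are split into pre-treatment and treatment-emergent** (Section 11.4.4.1), which partly separates pre-dose from on-drug ideation.
- **Rates may be lower.** Subjects are healthy volunteers screened on history, so the assumed episode rates may be too high; the protocol gives none.

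All of this limits the size and reach of the problem. It does not remove it. Deferring the baseline definition cannot create a matching pre-dose record, and with X blank nothing in the protocol secures the short window under which the difference would be nearly harmless. Equality with placebo holds in expectation; with 6 active and 2 placebo subjects per cohort, lifetime histories can differ by chance.

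**Conclusion.** The point holds in a limited form. The protocol names a change score that its own forms cannot support, because the only available baseline has a different recall window from every later value. The bias toward apparent improvement is material if the lifetime column serves as baseline, small with 6 to 12 months and negligible at about 1 month. Those sizes rest on assumed episode rates, severities and recall length; the direction follows from worst-in-window scoring. The pre-dose content of the first post-dose form rests on reading last visit as the last C-SSRS. The damage is to the within-group change summary, not to the visibility of individual cases nor, in expectation, to the comparison with placebo. In a descriptive Phase 1 study this is a minor but worthwhile correction.

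**What to change.** In Section 11.4.4.7, delete changes from baseline for the C-SSRS. In its place:

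1. Report, by treatment group, the number and percentage of subjects with any post-dose suicidal ideation (types 1-5) or suicidal behavior.
2. Report the number with treatment-emergent ideation or behavior, defined as new or worse than the recent column of the screening form. State the number of months for ideation, and the number of years for behavior, that are now blank on that form.
3. Show lifetime history separately, as background.
4. Use event dates to separate pre-dose from post-dose events on the first Since Last Visit form. The form has a date field only for actual attempts, so raters should note the onset of ideation in its description field or in the adverse event record.

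The cost is wording in the protocol and SAP plus a completion instruction for the form. No visit, assessment or subject is added. The recent window has to be set before Part B screening; if screening has begun, the SAP should state the window actually used.
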